Aim 1. Dependent and Independent Variables: The main dependent variable in Aim 1 is the preference for repair type (endovascular or open) as expressed by Veterans and surgeons in their respective survey instruments. Each survey instrument has a validated coding algorithm which will be used to categorize survey responses into preference for endovascular or open repair (Appendix 2)⁴⁴. Independent variables, such as age, gender, race, ethnicity, and other descriptive variables are recorded as part of the survey instrument by the Site Study Coordinator. Hospital and surgeon characteristics such as annual hospital and surgeon volume of endovascular and open repair for each participating site will be collected via VINCI by [name]. These variables will be measured at the hospital level, as in prior analyses.^{65, 97-100}

Aim 1: Data analytic strategy: tests, strengths, limitations, and alternative approaches: In Aim 1, our main outcome variable will be Veteran and surgeon preference for repair type (endovascular or open repair). The preference will be defined as either preference for endovascular or preference for open repair. Repair type preference will be categorized from several questions in our survey instruments. Several questions allow for differing degrees of choice (e.g., strongly/slightly favor open repair). For these responses, we will use variables that allow this category. We will use a coding algorithm (Appendix 2) which deconstructs survey questions into components that generate binary outcomes (i.e., preference for open or endovascular repair) and allows sensitivity analyses using the gradients. We will compare the proportion choosing each repair type in the intervention and control groups to test the effect of the decision aid on repair type preference. The proportions preferring each repair type will be compared between the two groups accounting for clustering of patients within center and/or surgeon; in particular, we will use the Mantel-Haenszel test (for stratified contingency tables, equivalent to partial likelihood ratio test from fixed effects logistic regression) or a mixed effects logistic regression with fixed effect of group, and random intercept for center effects.

Aim 1 Data Collection Strategy: potential problems and solutions Refer to Section 6 of this Protocol Coding Guide and Data Management Plan.

To identify patient characteristics (such as survey responses) associated with preference for endovascular or open repair we will use multivariable mixed effects logistic regression. The use of mixed effects is to account for clustering within individual VA centers using a random intercept, e.g. $\text{logit } \text{Pr}[Y_{ij}=1]=X_{ij}\beta+\mu_i$ where Y_{ij} is the binary preference variable in subject j from cluster i , X_{ij} is a vector of characteristics, μ_i is a random intercept from a zero mean distribution with standard deviation to be estimated (e.g. normal), and β is a vector of coefficient(s). We will explore the feasibility (e.g. convergence) and sensitivity of findings of patient characteristics of using either a random intercept for surgeon, or for center, or for surgeon nested within center. We will report both unadjusted and adjusted estimates, after identifying one or more models to adjust for using for instance stepwise regression or LASSO. Stata (e.g., xtmelogit) and/or R (library lme4 or nlme) software will be used. [name] has extensive experience in these strategies.

Missing Data: To accommodate missing data where justified (e.g. the variable with missing data is predictive and deserves to be adjusted for, and furthermore the data is believed to be missing at random) we shall use multiple imputation methods, such as implemented in the Stata *mi* routine.

Power Analysis: Comparing the effect of the decision aid on repair type preference. Because the decision aid will inform Veterans more fully about the long-term disadvantages of endovascular repair, we hypothesize that the decision aid will reduce the proportion of Veterans who prefer endovascular repair by 25%, based on similar decision aids studied in surgical settings in breast cancer and back pain¹⁶⁻¹⁸.

Table 3 Sample size and power calculations (assuming a 90% baseline rate of EVAR preference)

Number of clusters	Number of patients per cluster	Total Number of Patients	Proportion Choosing Endovascular Repair At	Decision Aid Effect Size (in relative decline in preference)	Proportion Choosing Endovasc Repair at	Power To detect significant difference	Power To detect significant difference	Power To detect significant difference
--------------------	--------------------------------	--------------------------	--	--	--	--	--	--

Intervention	Control	Intervention	Control	Intervention	Control	Control Sites for endovascular	Intervention Sites	(ICC 0.01)	(ICC 0.05)	(ICC 0.10)
10	10	12	12	120	120	0.9	0.25	0.68	0.96	0.86
10	10	12	12	120	120	0.9	0.20	0.73	0.88	0.75
10	10	12	12	120	120	0.9	0.15	0.78	0.71	0.50

We adjusted our sample size calculations for our cluster-randomized trial to account for intra-cluster correlation, and allow for variable enrollment size within each cluster. As shown in Table 8, we anticipate that we will have 96% likelihood of detecting a 25% effect size, assuming an ICC of 0.01. Sensitivity analyses around our ICC assumption of 0.01 demonstrate that even if our ICC is ten times higher (ICC=0.10), our sample size would still yield an 81% likelihood of detecting a 25% effect size between intervention/control.

Aim 2: To determine the effect of the decision aid on agreement between preferences and repair type.

Aim 2 Dependent and Independent Variables: After identifying Veterans' preference for endovascular or open repair, we will determine the agreement between their preferences and the repair types they receive. The dependent variable will be the kappa statistic (κ), measuring agreement between the preferred repair type and the repair type the Veteran ultimately receives. Cohen's kappa will be compared between the intervention and control groups. Kappa will be calculated overall and by hospital (using a weighted sum of the kappas for each hospital in that arm). As a secondary outcome, Site Study Coordinators will administer two surveys to the Veteran. These two surveys will examine patient satisfaction (PDQ-18) and shared decision making (Decision Process Score, or DPS)^{87, 104}. Our group has used these or similar instruments in prior work^{104, 105}. A survey administration training guide for each Site Study Coordinator has been developed. The DPS will be administered at the end of the visit, and the PDQ-18 will be completed at 30-day follow-up visits which are already standard practice after AAA repair for both repair types. Completing the surveys in this context will not require any extra visits by Veterans, an important strength given the elderly population of patients involved in our proposal.

Aim 2 Data Collection Strategy: potential problems and solutions: To inform the agreement between preference and repair type, we will compare the preference identified for each Veteran and the actual AAA repair type the Veteran receives at each site. We anticipate that 85% of Veterans will undergo repair within three months after the study visit in which they are enrolled. However, we estimate that 15% of patients will not undergo repair within 3 months of enrollment. Therefore, to ensure we capture the repair type for these patients, each Site Study Coordinator will audit CPRS every three months during the study period. At the end of the two years of audits, the site specific Site Study Coordinator will contact the enrolled patients via phone to ensure repair has not been performed outside of VA. Patients who do not undergo repair or who die prior to repair will be excluded. Sample size calculations incorporate a dropout rate of 10% for this effect. Re-survey will occur for a delay in repair greater than 3 months, if the pre-survey shows a change in Veteran repair preference from the original enrollment survey.

Aim 2 Data analytic strategy: After we have measured the necessary elements for agreement (preferences for repair type and the actual repair type), we will then calculate Cohen's kappa. We will stratify these analyses for surgeon agreement with the actual repair type (surgeon-preferred repair type matches the actual repair type, surgeon-preferred repair type does not match the actual repair type, and surgeon has no preference in repair type). Of note, Question #8 in the Decision Process Score allows us to measure incidents where discussion with the surgeon changed the Veteran's preference after the survey. We will perform sensitivity analyses including and excluding Veterans who changed preferences. To account for possible agreement of preference and choice with age, gender and race, we will estimate the association of choice with preference in a multivariable binary regression model that includes age, gender and race, and report the odds ratio (via logistic link) and rate ratio (via Poisson link). The fitted value from the logistic regression model will be used to calculate the four proportions used in the calculation of Kappa agreement using the method of average predictions (fitted values). Bootstrapping methods, as described by Efron and Tibshirani¹⁰⁶, will be performed if individual hospital samples are small.

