will use our secure VA Research Server under the direction of [name] as the Study Data Core. All study related committees will meet at the offices of the VA Outcomes Group, either in person or using existing secure teleconference facilities. Web-based study team meetings will be held every other week, and will use videoconference to minimize expense. Two study meetings will be held at the annual meetings of the Association of VA Surgeons and at the Society for Vascular Surgery during each year of the study. This will serve as a cost-effective way for our group to meet biannually during the study period.

Characteristics and selection of the study population: Our study population will be Veterans and vascular surgeons enrolled at the ten intervention sites and ten control sites in our cluster-randomized trial. The inclusion criteria for patients will be Veterans with a >5.0 cm AAA that are candidates for endovascular and open repair. Step C of the Study Procedures describe the recruitment procedures and inclusion criteria in detail.

STUDY PROCEDURES

Step A: Recruitment of Surgeons Twenty VA hospitals that currently perform both endovascular and open repair are the study sample. Each local site investigator has been interviewed and their credentials vetted by the PI, and has accepted to participate in the study. Local site investigators may invite one or two additional surgeons whom they work with at their site to participate in the study. Site Study Coordinators will provide surgeons the Study Invitation and Information Sheet at the start of the study period and document the date. A waiver of documentation of informed consent for surgeons will be requested since the surgeon's participation involves no procedures other than completion of a survey and presents no more than minimal risk.

Step B: Selection of Intervention Centers: In Aim 1, we will conduct the intervention in 120 patients across 10 VA hospitals randomly assigned to the intervention arm. We will have a 9:1 stratified randomization scheme, so that we have a similar proportion of Complex and Intermediate Surgical VA hospitals in the intervention and control arms. These are the only two types of VA hospitals that perform AAA repair. Sites will be randomized at IRB approval in a rolling fashion. Site specific Study Coordinators will use the Study Protocol to facilitate IRB approval.^{3, 15}.

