Step C: Recruitment of Patients: *We are requesting a waiver of informed consent for recruitment since potential participants will be identified through the screening process described as follows.*

- i. **Potential candidate referred to VA vascular surgery clinic.** The first contact with potential participants will occur when a referring physician indicates that they should be seen by a vascular surgeon for treatment of their AAA, and the patient is given an appointment for a consultation with a vascular surgeon at a study site.
- ii. **Identification of 12 Veterans with a >5.0 cm AAA who are candidates for endovascular and open repair.** The Site Study Coordinator will screen all new consultations made to VA vascular surgery clinics for Veterans with AAA that meet size criteria of ≥ 5.0 cm. Baseline audits at three clinics indicate ~15 new AAA referrals per vascular surgeon per month, and 60% of Veterans have an AAA that meets size criteria. Assuming a refusal rate of 50%, we anticipate we will enroll fully three months after enrollment begins, with a screening rate of 8 patients per site per month and an enrollment rate of four patients per site per month.
- iii. **Ensuring Veterans with AAA are candidates for both endovascular and open surgical repair.** Radiologic reports for new AAA consultations will be reviewed by the Study Coordinator according to the Site Recruitment Guide (Appendix 1). If a patient has an AAA that meets these size criteria (≥ 5.0 cm in diameter, the Study Coordinator will contact the Site Principal Investigator. The Site Principal Investigator will review imaging tests and the Veteran's electronic health record to ensure the Veteran is a candidate for endovascular and open repair using anatomic and clinical criteria defined according the Instructions for Use for each individual aortic endoprosthesis. These criteria derive from the Instructions-For-Use protocols determined by the

Food and Drug Administration⁸³. Site Principal Investigators will have discretion in interpretation for placement of an endovascular prosthesis outside of IFU guidelines. If the Veterans meets criteria for both open and endovascular repair, the Site Principal Investigator will inform the Study Coordinator.

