- iv. Inviting Veterans who are candidates to participate in the study: Once a candidate has been identified, the Study Coordinator will note the time of the Veteran's appointment. When the Veteran arrives for their appointment, they will check in as usual and proceed to the waiting room. The first contact with potential participants will be made by The Study Coordinator or other Study Team member who will take the Veteran to a consult room. Once in the consult room, the Study Coordinator or other Study Team Member will use the Study Introduction Script (Appendix 5), to describe the intervention to the Veteran (decision aid and survey) and invite them to participate. Veterans will be offered some time to review the consent form. If they wish to have more time to discuss it with their family and friends, they may reschedule their appointment and return on a later day. The Veteran will be informed that they will be remunerated \$50 at the completion of their first appointment for their time spent completing study documents and surveys.
- v. Consent process: Once a Veteran has expressed interest in the study, the Study Coordinator or other Study Team Member will review the consent form with them, answer any questions, and obtain consent. For any Veterans who are unable to read, the study coordinator will read the consent form to them in the presence of a witness. A witness is required to be present during the entire consenting process for illiterate participants and the witness will sign the informed consent to indicate he/she witnessed the participant "making their mark" consenting to be in the study. After consent has been obtained by the study coordinator, the Veteran will be taken through the survey process.

Step D: Survey administration at intervention and control sites:

Process at the Intervention Sites:

Step 1: The Pre-Survey will be administered with the Veteran by the Study Coordinator. (2 minutes)

Step 1a: The Study Coordinator will review the Decision Aid with the Veteran. (5-10 minutes)

Step 1b: The Study Coordinator will administer the Survey. (10 minutes)

Step 2: The Study Coordinator will escort the patient to the visit with the vascular surgeon.

Step 3: After the Visit, the Study Coordinator will complete the Decision-Process Score with the Veteran. (5 minutes)

Step 4: Thirty days after AAA repair, the Study Coordinator will complete the PSQ-18 with the Veteran. (5 minutes).

The decision aid is available in English and Spanish.

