The patient will be remunerated at completion of the enrollment visit. Data will be recorded securely by the Site Study Coordinator.

The Veteran will be thanked for their participation by the study team via a formal letter mailed from the Principal Investigator.

Process at the Control Sites:

Step 1: The Study Coordinator will administer the Survey. (10 minutes)

Step 2: The Study Coordinator will escort the patient to the visit with the vascular surgeon.

Step 3: After the Visit, the Site-Specific Research Coordinator will complete the Decision-Process Score with the Veteran. (5 minutes)

Step 4: Thirty days after AAA repair, the Study Coordinator will complete the PSQ-18 with the

Veteran. (5 minutes)

The patient will be remunerated at completion of the enrollment visit. Data will be recorded securely by the Site Study Coordinator.

The Veteran will be thanked for their participation by the study team via a formal letter mailed from the Principal Investigator.

Surgeon survey administration at both the intervention and control sites:

Step 1: The Study Coordinator will administer the Pre-Visit Survey to the surgeon (1 minute, according to pilot testing at four sites in the trial, and two sites outside the trial).

Step 2: The surgeon will have the clinic visit with the Veteran.

[figure not shown]
Step 3: After the Visit, the Study Coordinator will complete the Post-Visit Survey with the surgeon (1 minute).

Data will be recorded securely by the Study Coordinator.

Recruitment Target: We will recruit 12 Veterans per site (4 Veterans per site per month for 3 months) at 10 sites in the intervention arm for a total of 120 Veterans in the intervention arm. We will recruit 12 Veterans per site (4 Veterans per site per month for 3 months) at 10 sites in the control arm for a total of 120 Veterans in the control arm. The unit of analysis will be the Veteran. Randomization will occur at the site level, in a stratified 9:1 randomization scheme, based on the VA hospital's Surgical Complexity designation. We will enroll 8 Complex and 2 Intermediate sites per arm. Randomization will occur at the time of IRB approval. Weekly conference calls with Site Study Coordinators will assess study enrollment rates and help with problem-solving.

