Exclusion Criteria: Veterans with AAA who are not a candidate for both endovascular and open surgical repair will be excluded. Veterans who have already undergone AAA repair will be excluded. We will include Veterans who speak English and Spanish, using a translated survey instrument (Appendix 2). Veterans who cannot read will be offered participation by allowing the Site Study Coordinator to administer the survey.

Time Frame: Our study timeline is shown in Figure 6. IRB approval and site randomization will occur during the first 0-3 months of Project Year (PY1). Enrollment will begin at PY1 Month 3, and will be completed by the end of PY1 at all sites (a conservative estimate). After two-year follow-up on all sites in our cohort during PGY2-3, we will examine our final outcomes and complete reports and manuscripts in PY4.

Risk to Subjects (Veterans and Surgeon Participants).

Human Subjects Involvement and Characteristics.

Aim 1: Cluster-Randomized Trial of a Decision Aid and Survey (versus Survey alone) for different types of AAA Repair

In our study, we will identify Veterans presenting to Vascular Surgery Clinic with abdominal aortic aneurysms who are candidates for endovascular or open repair.

Sources of Materials.

Aim 1 and Aim 2 Survey Results

The materials for Aim 2 will be the results from our survey administered as described in Aim 1 and Aim 2. In accordance with our Data Management Plan, all will be coded to protect PHI, with study entrants being assigned a study identifier throughout the data management process. The study key that allows identification between individual study patients and their protected health information (PHI) will remain behind VA firewalls and will not be routinely used as part of the study analyses. We will create individual random identifiers for each study patient, and all study dates will be removed and replaced with time-to-event variables to limit any potential PHI contained in study datasets.

Potential Risks for Veterans.

Decision Aid and Survey

Our cluster-randomized trial will compare the effect of a patient educational tool (the decision aid) on survey responses describing patients' preferences for different types of AAA repair. Both types of AAA repair are commonly performed across VA, and both are commonly accepted alternatives for the treatment of AAA.

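### Veterans are selected and consented by site staff after their site has been allocated, but no pre-specified covariate-adjusted arm comparison is planned for Aim 1

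*Combined protocol and SAP*

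**What the plan says.** **Order of events (section 4, Steps B and C, Recruitment Target, Time Frame).** "Sites will be randomized at IRB approval in a rolling fashion". The Time Frame puts site randomisation in months 0 to 3 of the first project year and the start of enrolment at month 3. The only stratification factor is the hospital's surgical complexity: "We will enroll 8 Complex and 2 Intermediate sites per arm".

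**Who selects Veterans (Step C ii to v).** Screening is meant to be complete: "The Site Study Coordinator will screen all new consultations made to VA vascular surgery clinics for Veterans with AAA". The Site Principal Investigator then decides whether each Veteran is suitable for both repairs, with latitude: "Site Principal Investigators will have discretion in interpretation for placement of an endovascular prosthesis outside of IFU guidelines". The coordinator or another team member uses a script "to describe the intervention to the Veteran (decision aid and survey) and invite them to participate", and then takes consent. Half are expected to decline: "Assuming a refusal rate of 50%, we anticipate we will enroll fully three months after enrollment begins". At intervention sites the coordinator also goes through the aid with the Veteran (Step D).

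**How arms are compared (section 7, Aim 1 data analytic strategy).** The comparison of preference proportions is a Mantel-Haenszel test or a "mixed effects logistic regression with fixed effect of group, and random intercept for center effects". No Veteran characteristic is named, although age, gender, race and ethnicity are recorded.

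**Adjustment elsewhere.** The later Aim 1 paragraph on characteristics associated with preference promises unadjusted and adjusted estimates, with covariates found by methods such as stepwise regression or LASSO. In Aim 2, age, gender and race enter a regression of repair received on preference, whose fitted values feed kappa.

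**The concern.** Randomising 20 sites makes the sites comparable on average. It does not make comparable the Veterans whom those sites later judge eligible, approach and consent. If recruiters know the arm, the candidacy decision, the way the study is described and the Veteran's decision to join can each differ between arms. Any resulting difference in Veteran mix would be attributed to the decision aid in an analysis that holds only group and centre. A random centre intercept describes variation between sites; it does not remove a systematic difference between the two groups of sites.

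The Aim 1 outcome is Veteran preference, so whatever makes a Veteran with a particular leaning more likely to enrol in one arm acts directly on the estimate. The effect could go either way: a false finding for the aid, or a true effect partly hidden.

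**Working it through.** **1. Inputs from the plan.** Each arm has 10 sites of 12 Veterans, n = 120. Control EVAR preference is 0.90. The planned effect is a 25% relative decline, to 0.90 x 0.75 = 0.675 (printed as 0.68). ICC is 0.01, with 0.10 as the sensitivity value. Alpha for Aim 1 is not stated; two-sided 0.05 is assumed.

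**2. Reproducing the plan's power.** Effective n per arm = 120 / (1 + 11 x ICC).
- ICC 0.01: 120 / 1.11 = 108.1
- ICC 0.10: 120 / 2.10 = 57.1

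Standard error = sqrt[(0.90 x 0.10 + 0.68 x 0.32) / effective n], that is 0.0533 and 0.0734. The ratios 0.22 / SE are 4.12 and 3.00. A t-test on 20 - 2 = 18 degrees of freedom gives 97.4% and 80.9%, against the stated 96% and 81%. Both agree within 2 points, so the same set-up can be used below.

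**3. What a selection shift would do.** The plan gives no figure for the shift, so 2 and 5 points are assumptions. Suppose the aid has no effect but enrolled Veterans at intervention sites prefer EVAR less often than 0.90 because of who was enrolled. With d the shift:

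chance of a significant result favouring the aid = Phi[(d - 1.96 x SE0) / SE1],

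where SE0 uses the pooled proportion and SE1 the two separate proportions.

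| Shift | ICC | SE0 | SE1 | z | Chance (nominal 2.5%) |
|---|---|---|---|---|---|
| 2 points (0.88) | 0.01 | 0.0426 | 0.0425 | -1.49 | 6.8% |
| 5 points (0.85) | 0.01 | 0.0450 | 0.0449 | -0.85 | 19.7% |
| 2 points (0.88) | 0.10 | 0.0585 | 0.0585 | -1.62 | 5.3% |
| 5 points (0.85) | 0.10 | 0.0619 | 0.0617 | -1.16 | 12.4% |

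In the other direction, a true 22.5-point effect masked by 5 points (0.90 against 0.725) leaves power of 91.5% at ICC 0.01 and 67.3% at ICC 0.10 by the same formula.

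**4. Does the promised adjustment cover this?** The adjusted estimates come from a model whose stated purpose is to identify characteristics associated with preference. Arm is not named in it. Covariates are picked from the data, and the candidates include survey responses. At intervention sites the survey follows the aid (Step D), so such responses may already carry part of its effect. The Aim 2 regression concerns repair received and does not serve Aim 1.

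**5. Which covariates are usable?** Age, gender and race are recorded through the survey instrument, but the aid cannot change them. Diameter is on the radiology report read at screening. The Pre-Survey is listed only for intervention sites, so it cannot supply a baseline in both arms.

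**6. Room in the model.** Expected open-preferring Veterans under the planned effect: 120 x 0.10 + 120 x 0.32 = 12 + 38 = about 50 of 240.

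**7. Limit of adjustment.** Suppose 10% of candidates lean towards open repair and consent at 60% in one arm and 40% in the other, while the rest consent at 49% and 51%. Enrolled open-leaning shares are then 0.060 / (0.060 + 0.441) = 12% and 0.040 / (0.040 + 0.459) = 8%, a 4-point difference with no aid effect. Demographics and diameter would remove this only so far as they predict the leaning.

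**The case against.** The case on the other side has several sound parts.

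- **Adjustment is not absent from the plan.** It appears in the Aim 1 factor model and in Aim 2. This stands against any claim that nothing is adjusted. What is missing is a pre-specified adjusted arm effect for Aim 1.
- **Knowledge of arm by the Site Principal Investigator is inferred.** The text never states it. It follows from allocation by site before enrolment, with no masking described. For the coordinator at an intervention site it is certain, since that person delivers the aid. The enrolment guide and introduction script were not available to check.
- **There are safeguards.** All new consultations are screened, under the same written criteria in both arms. Bias is a risk, not a demonstrated fact.
- **Device-guideline discretion is a weak route for Aim 1.** A reader might infer from that sentence that discretionary cases shift the Aim 1 contrast substantially. The documents do not support this: Veterans state their preference before seeing the surgeon, nothing shows that they know their status under the device instructions, and no figure links that status to preference. It would also be a poor covariate. It is specific to each device, is not shown to be recorded as a field, and is set after allocation by the reviewer whose judgement is in question. Consent and refusal are at least as strong a route.
- **Chance differences between arms are not bias.** The centre effect and standard error are there to reflect them. Nor should precision be promised: in a logistic model, adjustment generally does not shrink the standard error of the log odds ratio, and it changes the estimand to a conditional one.

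**Conclusion.** The concern holds as a gap in the analysis plan. Veterans are selected after allocation by staff for whom no masking is described, and the Aim 1 arm comparison has no pre-specified adjustment for any Veteran characteristic. The promised adjusted estimates do not fill the gap, because they are not defined as an arm effect and their covariates are data-driven.

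The size is unknown. Under an assumed selection shift of 2 to 5 points, the chance of a false result favouring the aid rises from 2.5% to about 7-20% at ICC 0.01, or 5-12% at ICC 0.10. These figures rest on the assumed shift, a two-sided 0.05 test and the effective-n approximation.

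Two stronger readings should be resisted. The documents do not show that the Aim 1 result will be biased, and adjustment would not cure the problem: selection on unrecorded preference would largely remain.

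**What to change.** 1. In section 7, Aim 1, name one adjusted arm comparison: the stated mixed logistic model with group and random centre intercept, plus age, gender, race (coded sparingly) and AAA diameter from the screening radiology report.
2. Report the arm difference in proportions by standardisation: average the model's predicted probabilities over all enrolled Veterans under each arm and take the difference, with an interval that respects site clustering. Keep the unadjusted comparison alongside.
3. State that stepwise or LASSO selection, and any survey response taken after the aid, will not be used for this estimate. They may stay in the factor-finding model.
4. Carry the same covariates into the Aim 2 arm comparison, which means adding diameter to the age, gender and race already listed.
5. Tabulate screened, eligible, refused and enrolled Veterans by arm, and state as a limitation that selection on unmeasured preference cannot be adjusted away.

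**Cost.** SAP wording, one data field (diameter) from a report already read at screening, and a flow table. The model gains a few parameters with about 50 open-preferring Veterans expected, only about 12 of them in the control arm, which is why race should be coded sparingly.
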